1.2 Hypotheses

- Hypothesis 1: BWL treatment will be feasible and acceptable in autologous and allogeneic HSCT survivors.
- Hypothesis 2: Auto-HSCT and allo-HSCT survivors receiving BWL will have greater improvement in cognitive functioning than those receiving DRL.
- Hypothesis 3: The relationship between BWL and CRCI will be mediated by CAR and sleep.

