- 5) **Cognitive Screening (Screening):** Participants will be asked whether they have concerns about their cognition by asking a question derived from the two cognitive questions on the

PROTOCOL TITLE: Treating cognitive impairments in cancer patients via systematic light exposure

European Organization for Research and Treatment of Cancer Quality of Life Questionnaire (EORTC QLQ C-30).

- 6) **Neuropsychologically-assessed Cognitive Functioning (Times 1, 3, and 4):** Standardized neuropsychological tests will be used to evaluate multiple cognitive domains. They include all of the tests recommended by the International Cognition and Cancer Taskforce in their Lancet article⁶ chosen due to their frequent use in CRCI assessment and appropriateness for repeat assessments over time: a) Premorbid Intellectual Function will be assessed using the Wechsler Test of Adult Reading and the Vocabulary subtest of the Wechsler Adult Intelligence Scale - 4th Ed. (WAIS-IV) at Baseline only; b) Psychomotor vigilance will be assessed with the Psychomotor Vigilance Task; c) Attention will be assessed with the Digit Span subtest of the WAIS-IV;⁹⁹ d) Visual motor performance will be assessed with the Grooved Pegboard Test and Block Design subtest of the WAIS-IV; e) Visuospatial ability will be assessed with the Rey Complex Figure Test. f) Sustained attention and vigilance will be assessed with the Conners Continuous Performance Test 3rd Edition will be used to assess sustained attention and vigilance; g) Information processing will be assessed with Trail-Making Test A.¹⁰⁰ h) Processing speed will be measured with the Coding subtest of the WAIS-IV; i) Verbal fluency will be assessed with the Verbal Fluency subtest of the Delis-Kaplan Executive Function System (D-KEFS). j) Verbal learning and Memory will be assessed with the Hopkins Verbal Learning Test - Revised.¹⁰² k) Visual learning and memory will be assessed with the Brief Visuospatial Memory Test – Revised. l) Executive Function will be assessed with Trail-Making Test B¹⁰⁰ and the Paced Auditory Serial Addition Task¹⁰³ and the Stroop Color and Word Test.

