- 7) **Subjective Cognitive Function (Times 1, 2, 3, and 4):** The Cognitive Failures Questionnaire is a 25-item self-report measure of cognitive difficulties in everyday life using a 5-point Likert scale. Its reliability and validity are well-documented. Those who score ≥ 43 are deemed to have clinically significant impairment. This measure has been used widely in the measurement of cognitive assessment, including for cancer-related cognitive impairment (e.g., Calvio, Peugeot, Bruns, Todd, & Beuerstein, 2010; Scherling, Collins, MacKenzie, Lepage, Bielajew, & Smith, 2012). Patient Assessment of Own Functioning Inventory – a 33-item self-report measure of a patient's self-perceptions regarding their functioning in everyday tasks and activities.
- 8) **Neurobehavioral functioning (Times 1, 2, 3, and 4):** The Frontal Systems Behavior Scale is a reliable and valid measure of neurobehavioral functioning (Grace & Malloy, 2001)
- 9) **Sleep Quality (Times 1, 2, 3 and 4):** The Pittsburgh Sleep Quality Index consists of 19 self-rated items (35). Scale reliability is excellent using both an internal consistency criterion (Cronbach's alpha = 0.83) and test-retest reliability ($r = 0.85$). The validity of the instrument is based on its ability to discriminate patients (those having either sleep problems and/or depressive symptoms) from controls (healthy participants without sleep complaints).
- 10) **Chronotype (Time 1):** The Morningness-Eveningness Questionnaire: A reduced scale (MEQr) will be used to collect data on baseline circadian predispositions (Horne & Ostberg, 1976; Adan & Almirall, 1991). It is a 5-item self-rated survey designed to measure whether a person's peak alertness is in the morning or evening. This measure takes approximately 1 minutes to complete.
- 11) **Physical health (Time 1):** Physical health measures will be included as covariates in data analyses as they have been shown to be associated with fatigue, sleep, depressed

PROTOCOL TITLE: Treating cognitive impairments in cancer patients via systematic light exposure

mood, and cognition.⁵⁷⁻⁶⁶ We will include Body Mass Index (a measure of adiposity) calculated by dividing a participant's weight by the square of their height. The World Health Organisation classifies a body mass index of 25-29.9 as overweight, 30-34.9 as obese class I, 35-39.9 as obese class II, and ≥ 40 as obese class III.

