9.0 Data and Specimen Management

9.1 Data analysis plan

Descriptive statistics will be calculated for the entire group and separately for each treatment group. T-tests and Fisher's exact tests will be used to assess group differences at baseline for possible confounders (i.e., demographic variables, and clinical characteristics *including time since transplant*). Variables showing differences between the two groups will be used as covariates in subsequent analyses. Since there is no known seasonality effect on cognitive functioning, seasonality will not be controlled in these analyses.

Aim 1: Assess the feasibility and acceptability of BWL as an intervention for CRCI in HSCT survivors. Feasibility: We will adhere to currently accepted practice for feasibility studies¹¹⁰ by measuring the number of eligible patients, willingness of participants to be randomized, follow-up rates, the number who cease the intervention and their specific concerns about the intervention. We will monitor adherence by examining integrated meter data (i.e., time and duration of light box use). We expect high adherence, but if there is variation in duration, we will use duration as a predictor of the outcomes. Participants will be asked to log light box use (beginning and ending time) and reasons for not using it if that occurs. There is no gold standard for what constitutes a “feasible” study and relevant CRCI intervention feasibility studies have not been home-based.^{18, 111} Nevertheless, in an inpatient cognitive rehabilitation study of HSCT patients, 78% completed baseline, intervention, and time 2 assessments.¹⁸ A light exposure feasibility study for seasonal affective disorder deemed a 68% completion rate as acceptable,¹¹² and this is the criteria we will use in this study. In [name]'s pilot study, breast cancer

PROTOCOL TITLE: Treating cognitive impairments in cancer patients via systematic light exposure

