patients used the light box about 50% of the required days. This usage frequency was sufficient for cognitive improvement to occur in the BWL group. A 50% level of adherence will be considered acceptable in this study. Acceptability: As recommended in the literature, in addition to accrual rates, we will assess acceptability by evaluating participants' comments about the intervention after they have had experience with it.¹¹³ Finally, a comparison of the BWL and DRL on the FACIT-TS-G will be conducted using t-tests. Significant differences in favor of the BWL condition are expected.

Aim 2: Examine whether BWL compared with DRL among HSCT survivors suffering from cognitive impairment yields significant improvements in cognitive functioning. We will examine the cognitive functioning subscales and composite scores in separate analyses. Linear mixed model analysis with repeated measures will be conducted using the SAS procedure MIXED.

Contrasts will compare groups across assessments. The linear mixed model approach has a range of choices for the error variance/covariance structure and accommodates missing data thus protecting against a "completers only" bias. Since multiple outcomes will be correlated with one another, *p*-values for significance will be Sidak-adjusted for multiple comparisons. If there is variation in light box utilization, we will use duration time as a predictor of the outcome measures as in Aim 1. No pre-intervention bias favoring BWL over DRL is anticipated. However, we will test this assumption by crossing expectancy with the treatment condition. This interaction is not expected to be significant. These results will determine preliminary efficacy and sustainability of the intervention.

Power: Based on [name]'s pilot study with 10 breast cancer patients, the effect size indicated that we would need a sample size of 19 to achieve power at 0.80. However, the sample size is likely too small to provide reliable estimates of improvement in cognitive functioning. One of the main aims is to determine preliminary efficacy of the intervention in preparation for a larger scale trial. For a total sample of 80, we calculated the mean difference between the two treatment arms for the Neurocognitive (composite) Index and assumed a repeated measures design with an autoregressive lag 1 error structure and autocorrelation of 0.60. The difference able to be detected with power equal to 0.80 and alpha = 0.05, is 0.209.

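### Aim 2 does not say how the Time 1 cognitive score enters the mixed model or which contrast is the treatment effect; prespecifying baseline adjustment would gain precision without new data

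*Combined protocol and SAP*

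**What the plan says.** For Aim 2, Section 9.1 states: "Linear mixed model analysis with repeated measures will be conducted using the SAS procedure MIXED". The comparison of arms is then given in one sentence: "Contrasts will compare groups across assessments". No fixed effects are listed. The section does not say whether Time 1 is a response or a covariate, and no contrast is named as primary. Section 1.2 frames the hypothesis as change: survivors given BWL "will have greater improvement in cognitive functioning than those receiving DRL".

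Section 7.3 schedules the neuropsychological battery at Times 1, 3 and 4 and self-reported cognition at Times 1 to 4, so a Time 1 score is collected for both.

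Some covariates are planned. Section 9.1 tests demographic and clinical characteristics for baseline differences and then says: "Variables showing differences between the two groups will be used as covariates in subsequent analyses". Section 7.3 adds: "Physical health measures will be included as covariates in data analyses". Section 9.1 also brings in duration of light-box use if usage varies, and crosses expectancy with treatment. The outcome's own Time 1 score is not among these.

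For power, Section 9.1 "assumed a repeated measures design with an autoregressive lag 1 error structure and autocorrelation of 0.60", with 80 participants in total, and gives a detectable difference of 0.209 (repeated in Section 9.2).

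**The concern.** A mixed model with a free mean for each arm at each visit does not adjust for baseline in the way an analysis of covariance does. Its group-by-visit contrast against Time 1 is a difference in change; its group contrast at a later visit is a difference in level. Baseline adjustment has to be written in, either as a common baseline mean or as a Time 1 covariate.

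The covariate rule does not fill the gap. It would admit the Time 1 score only if that score counted as a clinical characteristic and happened to differ between arms on a test. Its value as a covariate comes from its correlation with later scores, which a baseline test does not measure.

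Cognitive functioning is the primary endpoint in Section 6.1, and with 80 participants precision limits what Aim 2 can show. Aim 2 also claims to address sustainability. That rests on Time 4, where the correlation with Time 1 is weakest and a change score performs worst.

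**Working it through.** **Inputs from the documents.** Total 80 (Sections 4.0 and 9.1); 40 per arm (Section 9.1, sleep and mood power); AR(1) with autocorrelation 0.60, alpha 0.05 and power 0.80 (Section 9.1); pilot difference 0.33 SD (Section 2.2).

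**Assumptions.** SD 1 at every visit, two-sided alpha, normal approximation, complete data, and Times 1, 3 and 4 as consecutive lags. The documents give neither the SD nor the number of assessments behind the power figure. The small cost of estimating the baseline slope is ignored.

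**The plan's own figure.** The detectable difference is (1.960 + 0.842) × SD × √(2v/40), where v is the variance of the contrast per participant. For a single visit v = 1, which gives 2.802 × 0.2236 = 0.626 SD. Across AR(1) contrasts of level, change and Time 1-adjusted level over two to four visits, the result runs from 0.45 to 0.78 SD. Slopes give 0.26 to 0.35 per visit. To obtain 0.209 from the non-slope contrasts, the index SD would have to be about 0.27 (0.209/0.784) to 0.46 (0.209/0.454). As no SD, scale, contrast or number of assessments is stated, 0.209 can be neither confirmed nor refuted, and it does not show which contrast was meant.

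**Three ways to compare the arms at one later visit**, with correlation r to Time 1:

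- level: v = 1
- change: v = 2(1 − r)
- Time 1-adjusted: v = 1 − r²

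The saving from adjustment is r² against level and (1 − r)/2 against change. Both are positive for any r strictly between 0 and 1.

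With r = 0.60 at Time 3 and 0.60² = 0.36 at Time 4, and SE = √(2v/40):

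| Visit | Contrast | v | SE | Detectable at 80% | Power for 0.33 SD |
|---|---|---|---|---|---|
| Time 3 | level | 1.00 | 0.224 | 0.626 | 31% |
| Time 3 | change | 0.80 | 0.200 | 0.560 | 38% |
| Time 3 | adjusted | 0.64 | 0.179 | 0.501 | 45% |
| Time 4 | level | 1.00 | 0.224 | 0.626 | 31% |
| Time 4 | change | 1.28 | 0.253 | 0.709 | 26% |
| Time 4 | adjusted | 0.87 | 0.209 | 0.584 | 35% |

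Power is Φ(0.33/SE − 1.96); for example, 0.33/0.179 = 1.845 and Φ(−0.115) = 0.45. A generalised least squares calculation over the three visits gives the same variances: 0.80 and 1.28 with free baseline means, 0.64 and 0.87 with a common baseline mean.

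**Variance savings:**

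- Time 3: 1 − 0.64/0.80 = 20% against change; 1 − 0.64 = 36% against level.
- Time 4: 1 − 0.87/1.28 = 32% against change; 1 − 0.87 = 13% against level.

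**Sensitivity to r:**

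- Lags counted over four visits (r = 0.36 at Time 3, 0.60³ = 0.216 at Time 4): 32% and 39% against change; 13% and 5% against level.
- r from 0.3 to 0.8: 35% down to 10% against change; 9% up to 64% against level.

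**A further risk of the open wording.** A group effect averaged over Times 1, 3 and 4 includes a visit with no treatment effect, so a sustained effect is diluted by one third. The variance of that mean is (3 + 2(0.6 + 0.6 + 0.36))/9 = 0.68. The detectable post-treatment effect is 2.802 × √(2 × 0.68/40) × 3/2 = 0.77 SD.

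**The case against.** The strongest reply is that the plan is silent here and has not chosen a poor method. The sentence on contrasts is compatible with a model that constrains the baseline means to be equal, and in that case nothing is lost. This stands. A reader might infer that the treatment effect will come from unadjusted contrasts, or that the sponsor has decided against using Time 1. The documents support neither inference: Sections 7.3 and 9.1 provide other covariates, and Section 9.1 does not say how Time 1 is handled. What remains is that the efficient analysis is not written down and the usual default parameterisation does not supply it.

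Second, a change contrast is unbiased under randomisation, and this is a feasibility and preliminary-efficacy trial. That also stands. The matter is efficiency, and at 0.33 SD power stays below one half even with adjustment.

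Third, the size of the gain depends on how lags are counted, which the plan does not state. This is correct, and it is why a range is shown.

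Fourth, a reader might extend the point to every repeated outcome as if all used the Aim 2 model. Section 9.1 says so only for the inflammatory markers. For sleep, fatigue and mood it refers to the Aim 1 strategy, which in the current numbering is feasibility. This may be old numbering, since Section 9.2 labels the cognitive power calculation as Aim 1, but the text does not settle it.

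**Conclusion.** The point holds as one of under-specification with a cost in precision. Section 9.1 names neither the treatment contrast nor the role of the Time 1 score. Under either natural reading the estimate is valid but less precise than a baseline-adjusted one. The percentages in the working rest on SD 1 at each visit, 40 per arm, complete data and the lag count; the powers also ignore the planned Sidak adjustment, which would lower all of them. The ordering, with the adjusted contrast the most precise, needs only equal variances across visits and a correlation between 0 and 1. The plan should be amended, but nothing here suggests bias or threatens the trial's validity.

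**What to change.** In Section 9.1, Aim 2, specify a constrained longitudinal model regardless of any baseline test: Times 1, 3 and 4 as responses, visit effects, one baseline mean common to both arms, treatment-by-visit terms only after baseline, and a named covariance structure. Report the BWL minus DRL difference at Time 3 and at Time 4, and say which is primary.

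This form also keeps participants with partial data. A model with Times 3 and 4 as responses and Time 1-by-visit as covariate is a close alternative when data are complete, but with missing scores the two can use different participants.

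Apply the same principle to the other repeated outcomes on their own schedules: four visits for self-reported cognition, sleep quality, fatigue and mood; one post-baseline draw for the markers. Correct the reference to the Aim 1 strategy in the sleep and mood paragraph of Section 9.1.

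State that Time 1 testing precedes allocation. Section 20.1 implies this by listing baseline assessment before randomisation, but Sections 3.1 and 7.1.1 mention random assignment before describing Time 1.

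The cost is SAP wording and a few lines of PROC MIXED code. No new data are needed, provided Time 1 is scored before allocation.

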6.0 Study Endpoints

6.1 The primary endpoints in the proposed study are: 1) the level of cognitive functioning (as measured by the neuropsychological tests and self-reported cognitive functioning using the PAOFLI)

Secondary endpoints are: 1) Circadian activity rhythms using an actigraph (a small device similar in size to a watch that measures sleep and wake activity); 2) The Pittsburgh Sleep Quality Index; 3) the FACIT Fatigue Scale; 4) Quality of Life measured by the SF-36 scale; 5) a Credibility/Expectancy Questionnaire; 6) levels of Inflammatory Immune Markers; 7) the amount of time that the light boxes are used; 8) treatment satisfaction using the FACIT-TS-G scale; 9) depressed mood as measured by the CES-D; and 10) neurobehavioral functioning as measured by the Frontal Systems Behavior Scale.

6.2 With regard to safety endpoints, there are no known risks associated with the use of the light boxes in the treatment of cognitive impairments. However, we will monitor those who decide to cease treatment because they find the treatment approach unacceptable along with their concerns regarding treatment.

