Aim 3: Examine whether BWL compared with DRL affects sleep and psychological variables (depressed mood, fatigue) which have been implicated as correlates of cognitive functioning in cancer patients. Hypothesis 2: Sleep quality and psychological variables will improve in the BWL group compared to the DRL group. The Aim 1 analytic strategy will be used in the analysis of this aim. Power: Our preliminary R-21 study that examined BWL vs. DRL on cancer-related fatigue in a mixed cancer population (including HSCT) provided guidance for the power. Sleep Quality: While survivors in the BWL group had better sleep quality scores than the DRL group, the main effect for treatment was not statistically significant, no doubt due to sample size. Cohen's *d* was 0.63. For a repeated measures design with alpha equal to 0.05 and a sample size of 40 per group, power=0.99. CAR: There was significant time x treatment interaction (*p*=0.02) on the F statistic. We calculated power for a repeated measures design with autoregressive lag 1 structure and autocorrelation of 0.60. With alpha equal to 0.05 and sample size of 40 per group, power=0.99. Fatigue: As with CAR, there was significant time x treatment interaction (*p*=0.003). Using the same method as above, power = 0.99. Depressed mood: There was a significant (*p*=0.004) time x treatment interaction. Using the same method as above, power = 0.99.

Exploratory Aims: Explore a) whether BWL compared with DRL affects biological (inflammatory immune response) variables; and b) whether the effects of BWL compared to

PROTOCOL TITLE: Treating cognitive impairments in cancer patients via systematic light exposure

DRL on cognitive functioning are mediated by sleep, chronobiological factors (i.e., circadian activity rhythms), biological factors (i.e., inflammatory immune response), and psychological factors (i.e., fatigue, depressed mood).

- a) Assess whether the BWL intervention affects biological factors (IL-1ra, IL-6, IL-8, IL-10, sTNF-III, CRP, PBMCs, and intracellular RNA) that have been identified as correlates of CRCI. Biological variables will be measured at Times 1 and 2. The mixed linear model approach described in Aim 2 will be used here.

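### Sidak adjustment is justified by correlation rather than by the number of tests, its form and family are undefined, and the composite is powered at an unadjusted 0.05

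*Combined protocol and SAP*

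**What the plan says.** Section 9.1 (Data analysis plan, Aim 2) sets up the cognitive comparison in three statements:

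- **Outcomes:** "We will examine the cognitive functioning subscales and composite scores in separate analyses". Each analysis is a linear mixed model with contrasts between groups across assessments.
- **Multiplicity:** "Since multiple outcomes will be correlated with one another", the p-"values for significance will be Sidak-adjusted for multiple comparisons".
- **Power:** "For a total sample of 80, we calculated the mean difference between the two treatment arms for the Neurocognitive (composite) Index", assuming "an autoregressive lag 1 error structure and autocorrelation of 0.60". The result is: "The difference able to be detected with power equal to 0.80 and alpha = 0.05, is 0.209". Section 9.2 repeats it.

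Section 6.1 defines the primary endpoint as "the level of cognitive functioning (as measured by the neuropsychological tests and self-reported cognitive functioning using the PAOFLI"). Section 7.3, item 6, lists the neuropsychological battery. After the baseline-only premorbid measure there are 11 domains (b to l), covering 14 repeated tests. The group size comes from the power text for Aim 3 in Section 9.1: "sample size of 40 per group".

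The plan does not state the number of tests in the Sidak family, whether the composite or the individual time contrasts belong to it, whether the procedure is single-step or step-down, or any correlation between outcomes.

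**The concern.** Correlation is not a reason to choose Sidak. Multiplicity comes from the number of tests. The Sidak level 1 - 0.95^(1/m) gives a family-wise error of exactly 5% when the m tests are independent, and less than 5% when they are positively correlated. Subscales, and a composite built from them, will be correlated. Someone who took the stated reason at face value would believe that the method makes use of the correlation, which it does not.

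The more practical issue is the gap between the power statement and the analysis rule. The composite is the only cognitive outcome with a power figure, and that figure uses alpha 0.05. Nothing in Section 9.1 takes the composite out of the adjusted set. If it is in the set, it will be tested at a much smaller alpha than the one it was powered for, in a study of 40 per arm meant to inform a larger trial.

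**Working it through.** **Inputs.** From the plan: N = 80, 40 per group, alpha 0.05, power 0.80, detectable difference 0.209, AR(1) autocorrelation 0.60. Assumed: two-sided testing, the number of tests m, and a between-outcome correlation rho. The plan's 0.60 is a correlation over time within one outcome and cannot serve as rho. For m, 2 is a small family, 12 is the 11 repeated domains plus the composite, and 14 is the number of repeated tests.

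**1. The plan's own figure.** The 0.209 cannot be reproduced, because no SD is given for the composite. In SD units the detectable difference is (1.960 + 0.842) × sqrt(2v/40), where v depends on the contrast:

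| Contrast | v | Detectable (SD) | SD implied by 0.209 |
|---|---|---|---|
| Single time | 1 | 0.63 | 0.33 |
| Mean of three times | 0.68 | 0.52 | 0.40 |
| One follow-up, baseline-adjusted | 0.64 | 0.50 | 0.42 |
| Change over two lags | 1.28 | 0.71 | 0.30 |

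The figure is therefore compatible with a composite SD of about 0.30 to 0.42. Step 2 needs only ratios, so it does not depend on which contrast was used.

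**2. The composite inside the family.** Per-test alpha is 1 - 0.95^(1/m), with two-sided critical value z_m. Power for the planned effect is Φ(1.960 + 0.842 - z_m). The detectable difference is 0.209 × (z_m + 0.842)/2.802.

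| m | alpha per test | z_m | Power | Detectable difference |
|---|---|---|---|---|
| 1 | 0.0500 | 1.960 | 0.80 | 0.209 |
| 2 | 0.0253 | 2.236 | 0.71 | 0.230 |
| 12 | 0.0043 | 2.858 | 0.48 | 0.276 |
| 14 | 0.0037 | 2.906 | 0.46 | 0.280 |

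At m = 12 the factor is (2.858 + 0.842)/2.802 = 1.32. These powers hold for single-step Sidak, and for step-down when nothing else has been rejected first. No between-outcome correlation is needed.

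**3. How conservative Sidak is under correlation.** Simulation of 11 equally correlated domain statistics plus their standardised mean (12 tests, no true effects) gives family-wise error of about 0.044, 0.036 and 0.027 at rho 0.3, 0.5 and 0.7. Control holds throughout. In an equicorrelated family of 11 to 16 outcomes, an exact single-step method that uses the correlation would gain about 1 point of power per outcome at rho 0.3, about 4 at 0.5 and 5 to 6 at 0.6.

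**4. What step-down adds.** Same 12-test setting, rho 0.5, d = 0.5 in each responding domain. Share of true domain effects found:

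| Domains responding | Single-step | Step-down |
|---|---|---|
| 1 | 0.27 | 0.27 |
| 3 | 0.27 | 0.27 |
| 5 | 0.27 | 0.28 |
| 11 | 0.27 | 0.34 |

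With all 11 responding and the composite kept in the family, composite power is 0.57 single-step and 0.58 step-down. Tested alone at 0.05 it is 0.86.

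**5. Putting the composite first.** If the composite is tested at 0.05 and the subscales are tested by Holm-Sidak regardless of its result, overall family-wise error with no true effects is about 0.077, 0.065 and 0.056 at rho 0.3, 0.5 and 0.7. If the subscales are tested only after a significant composite, the share of true effects found at rho 0.5 is about 0.11 when 3 of 11 domains respond and 0.19 when 5 do, against 0.27 under single-step Sidak.

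**The case against.** The best defence is that the plan's method is valid. Sidak keeps family-wise error at or below 5%, the aim is preliminary efficacy, and mild conservatism is defensible. All of that stands.

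Several stronger readings are tempting but not supported:

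- **That the plan uses single-step Sidak and wastes power.** The plan says only that p-values are Sidak-adjusted; step-down Sidak also fits those words. The loss due to correlation depends on m and rho, neither of which is given, and is about 1 point at rho 0.3.
- **That the composite is certainly in the family.** Separate analyses and a power figure at 0.05 are equally consistent with its being outside. The results in step 2 are conditional on inclusion.
- **That 0.57 versus 0.86 measures Sidak's cost under correlation.** That gap comes from taking the composite out of the family. The drop from 0.80 to 0.48 is likewise the price of 12 tests.
- **That a better procedure is free and exploits the correlation.** Step-down Sidak does not use the correlation and gives up simple simultaneous confidence intervals. Resampling max-T does use it, but needs joint resampling across separately fitted mixed models with missing data. Testing the composite first is a trade-off, as step 5 shows.

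**Conclusion.** The point holds as one of specification and efficiency. The stated reason for Sidak is wrong, the form and family of the adjustment are undefined, and the power figure and the analysis rule do not visibly agree.

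The size depends mainly on whether the composite is in the family. If it is, planned power of 0.80 becomes 0.71 with 2 tests, 0.48 with 12 or 0.46 with 14. If it is not, the 0.209 is unaffected by multiplicity and only the wording needs repair. These figures rest on assumed m and two-sided normal tests.

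The gain from naming step-down is near zero when few domains respond and about 7 points per domain if all 11 do, at an assumed rho of 0.5 and d of 0.5. A reader might infer a type I error flaw; there is none, since Sidak errs on the conservative side under positive correlation.

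**What to change.** 1. **Name the procedure and the family.** List the cognitive outcomes and contrasts to be adjusted, and specify step-down Holm-Sidak for them. It never rejects less than single-step Sidak and controls family-wise error at the same 5% level. The cost is one sentence, a short piece of code, and the loss of simple simultaneous confidence intervals.
2. **Make power and analysis agree**, by one of two routes:
   - Keep the composite in the family and restate the detectable difference at the adjusted alpha in Sections 9.1 and 9.2 (about 0.276 if there are 12 tests). This costs a recalculation and a less favourable figure.
   - Declare the composite the single primary test at 0.05, so that 0.209 keeps its stated alpha. Align Section 6.1 with this, say whether subscale tests are gated on the composite, and state the overall error. Without gating, overall error exceeds 5%; with gating, effects confined to a few domains are more often missed.
3. **Delete correlation as the reason for Sidak** and give the number of tests instead.

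Resampling max-T is optional. It is the remedy that uses the correlation, but it needs joint resampling across the mixed models and relies on a correlation estimated from 80 participants.
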